- z* **Disease Assessment:** All lab tests include M-protein quantification (serum and 24-hour urine, immunoelectrophoresis, and immunofixation) and serum free light chain levels should be repeated on C1D1 if not performed within 3 days prior to first IMP administration, and all radiologic assessments to be performed within 21 days prior to first IMP administration. Response is assessed on the basis of clinical and laboratory findings on D1 of every cycle (starting C2, prior to IMP administration), whenever disease progression is suspected (eg, symptomatic deterioration) and at the EOT visit. The availability of the results must not prevent the initiation of the next cycle.
- aa* **Serum M-Protein:** To be performed at Screening, D1 of every cycle prior to IMP administration (not required to be repeated at Cycle 1 if screening labs were performed within 3 days prior to first IMP administration), and at the EOT visit. Immunofixation to be performed at baseline and required after treatment due to disappearance of the M component in the electrophoresis. An additional serum sample will be collected at all time-points to evaluate the potential interference of isatuximab in the M protein assessment (central laboratory).
- bb* **sFLC:** To be performed at Screening, D1 of every cycle prior to IMP administration (not required to be repeated at Cycle 1 if screening labs were performed within 3 days prior to first IMP administration), and at the EOT visit.

- cc* **Urine M-Protein (24-hr urine):** 24-hour urine collection for Bence Jones protein with urine electrophoresis at Screening, D1 of every cycle prior to IMP administration (not required to be repeated at Cycle 1 if screening labs were performed within 3 days prior to first IMP administration), and at the EOT visit. Urine immunofixation to be performed in this 24 hours urine at baseline and if required due to disappearance of the M component in the electrophoresis. If negative at baseline, to be repeated every 3 months and to confirm response or PD.

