9.2 EFFICACY

9.2.1 Primary endpoint (Phase 2 only)

The second co-primary endpoint of the study is to determine the efficacy of the combination as assessed by ORR. ORR is defined as the proportion of patients with CR (including sCR), VGPR and PR as assessed by investigators using the IMWG response criteria (44).

The following disease assessment procedures will be performed at screening (for eligibility) and again at Cycle 1 Day 1 prior to study treatment administration (baseline for response assessment) and then Day 1 of every cycle during treatment up to progression:

- M-protein quantification (serum and urine) (local laboratory).
- FLC quantification (local laboratory).
- Quantitative immunoglobulins (local laboratory).

- In addition, other examinations for disease assessment will be done as clinically indicated (eg, to confirm a response, suspected PD) as below (local laboratory):
 - Bone marrow aspiration,
 - Bone disease assessment,
 - Extramedullary disease (plasmacytoma) assessment (including bone plasmacytoma).

Response/progression will be determined according to IMWG criteria (44) ([Appendix D](#)). Response/progression based on M-protein and FLC will be confirmed based on 2 consecutive assessments.

Progressive disease is defined for patients with measurable disease with one of the following:

- Increase of $\geq 25\%$ in serum M-protein from nadir (the absolute increase must be ≥ 0.5 g/dL) in 2 consecutive assessments; serum M-protein increases ≥ 1 g/dL in 2 consecutive assessments are sufficient to define relapse if starting M-protein t is ≥ 5 g/dL and/or,
- Increase of $\geq 25\%$ in urine M-protein from nadir (the absolute increase must be ≥ 200 mg/24 h) in 2 consecutive assessments and/or,
- Only in subjects without measurable serum and urine M-protein levels: increase of $\geq 25\%$ in the difference between involved and uninvolved FLC levels and absolute increase must be > 10 mg/dL and/or,
- Definite development of new bone lesions or soft tissue extramedullary disease, or increase $\geq 50\%$ from nadir in the sum of perpendicular diameters of existing soft tissue extramedullary disease lesions if > 1 lesion, or $\geq 50\%$ increase in the longest diameter of a previous soft tissue extramedullary disease lesion > 1 cm in short axis.

Clinical deterioration will not be considered progression in the primary analysis of ORR.

Measurable disease is defined by at least one of the following measurement:

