Progressive disease	
Any one or more of the following criteria: Increase of $\geq 25\%$ from lowest confirmed value in any one of the following criteria:
 
 • Serum M-protein (the absolute increase must be ≥ 0.5 g/dL) • Serum M-protein increase ≥ 1 g/dL if the lowest M component was ≥ 5 g/dL • Urine M-component (the absolute increase must be ≥ 200 mg/24 h) • In patients without measurable serum and urine M-protein levels, the difference between involved and uninvolved FLC levels (absolute increase must be > 10 mg/dL) • In patients without measurable serum and urine M-protein levels and without measurable involved FLC levels, bone marrow plasma-cell percentage irrespective of baseline status (absolute increase must be $\geq 10\%$) • Appearance of new lesion(s), $\geq 50\%$ increase from nadir in SPD of > 1 lesion, or $\geq 50\%$ increase in the longest diameter of a previous lesion > 1 cm in short axis; $\geq 50\%$ increase in circulating plasma cells (minimum of 200 cells per μL) if this is the only measure of disease 
Two consecutive assessments are needed. No known evidence of progressive disease or new bone marrow lesions if radiographic studies were performed

Abbreviations: CR, complete response; FLC, free light chain; IMWG, International Myeloma Working Group; M, monoclonal; MRD, minimal residual disease; NGF, next-generation flow; NGS, next-generation sequencing; PD, progressive disease; PR, partial response; sCR, stringent complete response; SD, stable disease; SPD, sum of the products of the maximal perpendicular diameters of measured lesions; SUV, maximum standardized uptake value; VGPR, very good partial response.

A plasmacytoma that has been radiated is not suitable for response assessment; however, it must be monitored to assess for progressive disease.

For patients achieving very good partial response by other criteria, a soft tissue plasmacytoma must decrease by more than 90% in the sum of the maximal perpendicular diameter (SPD) compared with baseline.

Definite increase in the size of existing bone lesions or soft tissue plasmacytomas is defined as below: $\geq 50\%$ increase in the size of at least one bidimensionally measurable lesion (in comparison with the measurements at Nadir) or appearance of a new lesion. Pathological fracture or collapse of bone are not necessarily evidence of disease progression.

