Reminder: definitions of Response and Progression are based on IMWG Uniform Reporting Criteria:

- Any response (sCR, CR, VGPR, PR) or progression needs to be confirmed by two consecutive disease assessments according to the Study Flow Chart. A disease assessment at one time point not matched by the same disease assessment at the next time point will be considered unconfirmed (except for progression by imaging, bone marrow PC counts, where one time point is adequate for confirmed progression).
- Urine M-protein is not needed to document partial response or minor response if baseline urine M-protein was not measurable; however, it is still required for complete response and very good partial response.
- Serum FLC levels should only be used for response assessment when both the serum and urine M-component levels are deemed not measurable.
- Documentation of response requires two consecutive readings of the applicable disease parameter (serum M-protein, urine M-protein), performed at any time (no minimum interval is required, it can be done the same day); however, to confirm response or progressive disease, two discrete samples are required; testing cannot be based upon the splitting of a single sample.
- Patients will continue in the last confirmed response category until there is confirmation of progression or improvement to a higher response status; patients cannot move to a lower response category.
- Percent decreases for response calculations are from baseline values (Cycle 1, Day 1).
- Percent increases for progression calculations are from lowest response values or baseline values, whichever is the smaller number. The lowest value does not need to be confirmed.
- The lowest value before suspected progression will be used for calculation of progression; if a serum and/or urine spike is considered too low to quantitate, this value can be assigned as zero as a baseline for documentation of subsequent progressive disease. Patients will be considered to have progressive disease if they meet the criteria for progression by a variable that was not considered measurable at baseline; however, for patients who had a measurable serum or urine M-spike at baseline, progression cannot be defined by increases in serum FLC alone.

Appendix E Guidelines for the determination of the number of prior lines of therapy in multiple myeloma

Line of Therapy

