2.1.3 Efficacy endpoints

Response assessments were to be performed on Day 1 of every cycle during treatment by investigators using the International Myeloma Working Group (IMWG) response criteria (1) and by considering the assessment included in Section 1.4.

Biological responses (\geq PR) and progression should be confirmed on 2 consecutive biological (serum and/or urine M protein) disease assessments. No confirmation is required for radiological assessment.

For Phase 1, best overall response, duration of response, progression free survival and overall survival will be derived and listed by patient.

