2.1.3.1 Primary efficacy endpoint (Phase 2 only)

The primary efficacy endpoint is ORR, defined as the proportion of patients with CR (including sCR), VGPR or PR as BOR as assessed by the investigator. BOR will be derived using disease assessments (overall response CRF page) from the start of treatment through the entire study excluding any assessments performed after disease progression (that is confirmed), the cutoff date or following the start of further therapies for MM (see Figure 1). The ordering of evaluations from best to worse is: sCR, CR, VGPR, PR, MR, stable disease (SD), progressive disease (PD), not evaluable (NE). BOR for patients without response assessment will be 'Not evaluable'. BOR will be the best sequential response based on the investigator's disease assessments as determined by the criteria in Table 3. In addition, the following rules will be applied:

- BOR will be NE for patients who received at most 2 isatuximab administrations with investigator assessment of response of SD or better at Cycle 1 or end of treatment.
- BOR will be PD for patients without response assessment who received 1 cycle of treatment and died due to PD or had symptomatic deterioration within 30 days of last study treatment administration.

Symptomatic deterioration will not be considered as progression in the primary analysis of ORR.

Table 3 - Sequential response determination for investigator response assessment

Overall response at Cycle n	Overall response at Cycle n+1 ^a	Sequential response
sCR	sCR	sCR
CR	sCR	CR
sCR	CR	CR
CR	CR	CR
sCR/CR	VGPR	VGPR ^b
sCR/CR	PR	PR
VGPR	sCR/CR/VGPR	VGPR ^b
VGPR	PR	PR

Overall response at Cycle n	Overall response at Cycle n+1 ^a	Sequential response
PR	sCR/CR/VGPR/CR/PR	PR
sCR/CR/VGPR/PR	NE/No further evaluation/SD/PD	MR ^c
MR	Any	MR
Any	MR	MR
NE/SD/PD	sCR/CR/VGPR/PR	MR ^c
NE/PD/SD	SD	SD
SD	No further evaluation/NE/PD	SD
NE	SD	SD
PD	No further evaluation/NE	unPD ^e
PD	PD	PD
NE	PD	unPD ^e
NE	No further evaluation	NE
No evaluation ^d		PD ^d

a Disease assessment are planned to be performed every cycle. Disease assessment performed after the start of new anticancer treatment will be excluded from the derivation of BOR.

b Sequence provided for programming purpose.

[figure not shown]
c Unconfirmed PR or CR will be considered MR.

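### Protocol Appendix D gives two conflicting reference values for progression (lowest confirmed value, and lowest value confirmed or not), so one M-protein series can give two progression dates

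*Protocol*

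**What the plan says.** Four places in the current text bear on the value from which a rise is measured.

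- **Protocol Appendix D, progressive disease row.** The increase of at least 25% is taken "from lowest confirmed value in any one of the following criteria". For serum M-protein the absolute rise must also be at least 0.5 g/dL. The row separately asks for two consecutive assessments.
- **Protocol Appendix D, reminder list.** "Percent increases for progression calculations are from lowest response values or baseline values, whichever is the smaller number". The same bullet continues: "The lowest value does not need to be confirmed". The next bullet adds: "The lowest value before suspected progression will be used for calculation of progression".
- **Protocol Section 9.2.1.** The rise is measured "in serum M-protein from nadir", and must be present on two consecutive assessments. Nothing is said about confirming the nadir.
- **SAP Section 2.1.3.** Biological responses "and progression should be confirmed on 2 consecutive biological (serum and/or urine M protein) disease assessments". This confirms the event. It does not address the reference value.

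On timing, footnote z of the study flowchart (Protocol Section 1.1) states: "Response is assessed on the basis of clinical and laboratory findings on D1 of every cycle", starting at Cycle 2. The SAP uses the investigator's assessments.

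**The concern.** Two rules in one appendix answer the same question in opposite ways, and neither the protocol nor the SAP ranks them. The adjective in the table row qualifies the reference value, not the progression event, because the row states its two-assessment requirement separately. With one planned response assessment per cycle, a patient's lowest reading can be a single value that the next visit does not repeat. An investigator working from the table and one working from the reminder list could then record different progression dates, or progression against none.

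The progression date enters PFS and DOR directly. It can also reach best overall response, and so ORR, because SAP Section 2.1.3.1 derives that response "excluding any assessments performed after disease progression (that is confirmed". A confirmed response that first appears after an early rebound counts under one rule and is lost under the other.

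**Working it through.** The plan states no figure that depends on the reference value. Its 79% power for ORR recomputes to 0.791 but plays no part here. The check applies both rules to the same serum M-protein series. All series are illustrative, not trial data.

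**Threshold.** For a reference x below 5 g/dL, progression needs a value of at least T(x) = max(1.25x, x + 0.5). The two parts cross at 0.5 / 0.25 = 2.0 g/dL. Progression is dated at the first of two consecutive values at or above T(x).

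**Direction.** A confirmed reference cannot lie below the lowest value, and T rises with x. The table row can therefore only delay or remove progression. If the confirmed reference is higher by d, the threshold rises by d when both references are at or below 2 g/dL, by 1.25d when both are at or above 2 g/dL, and by an amount in between otherwise.

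**Readings of *confirmed*.** The protocol does not define the word for a reference value, so four readings were tried:

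1. the higher of the lowest consecutive pair;
2. the mean of the lowest consecutive pair;
3. the lowest value followed by one no more than 10% higher;
4. the lowest value whose response category is matched at the next visit, which borrows the reminder list's notion of an unconfirmed assessment.

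**Series 1: 1.0, 1.0, 0.6, 1.1, 1.1 g/dL.**
- Lowest value: T(0.6) = max(0.75, 1.1) = 1.1. Visits 4 and 5 both reach it, so progression is at visit 4.
- Readings 1 and 3: T(1.0) = max(1.25, 1.5) = 1.5, never reached.
- Reading 2: reference (1.0 + 0.6)/2 = 0.8, T = max(1.0, 1.3) = 1.3, never reached.
- Reading 4: 0.6 is a 40% reduction (minimal response) and 1.1 is above baseline, so the low is unmatched. The reference stays 1.0 and there is no progression.

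**Series 2: 3.0, 2.0, 2.0, 1.5, 2.0, 2.1, 2.3, 2.5, 2.6 g/dL, Cycle 1 Day 1 (C1D1) to C9D1.**
- Lowest value: T(1.5) = max(1.875, 2.0) = 2.0. C5D1 (2.0) and C6D1 (2.1) reach it, so progression is at C5D1.
- Readings 1 and 3: T(2.0) = 2.5. C8D1 (2.5) and C9D1 (2.6) reach it, so progression is at C8D1.
- Reading 2: reference (2.0 + 1.5)/2 = 1.75, T = max(2.1875, 2.25) = 2.25, giving C7D1.
- Reading 4: 1.5 is a 50% reduction (partial response) and the following 2.0 is 33% (minimal response), so the low is unmatched. The reference is 2.0, giving C8D1.
- In 28-day cycles the gap is 3 × 28 = 84 days, or 2 × 28 = 56 days under reading 2.

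**Control: 3.0, 2.0, 1.5, 1.5, 2.0, 2.1, 2.5, 2.6, 2.7 g/dL.** The low is repeated. The reference is 1.5 and progression is at C5D1 under both rules and all four readings.

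**Route to best overall response: 2.4, 1.6, 1.6, 1.25, 1.8, 1.8, 1.1, 1.0 g/dL.**
- From the lowest value, T(1.25) = 1.75 and progression is at C5D1. The best earlier reduction is 1 − 1.25/2.4 = 48% (minimal response).
- Under readings 1 to 3 the thresholds are 2.1, 1.925 and 2.1, so there is no progression. The later 54% and 58% reductions then count as partial response.
- Under reading 4 the rules agree: 1.8 is exactly 25% below 2.4, still minimal response, so the low is matched.

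**The case against.** The best defence is that the text as a whole points one way. The reminder list is the only place that addresses whether the reference needs confirming, and it says no. Its next bullet and Section 9.2.1 agree. Within the row itself, the criterion for M-protein of 5 g/dL or more and the lesion criterion use unqualified terms. One stray adjective stands against several consistent statements. That identifies the likely intention and the right correction. It does not remove the conflict, because the contrary rule sits in the criteria table and nothing says that the list overrides it.

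A second objection concerns how far the disagreement reaches, and it stands. A reader might infer that any single low reading followed by a rise gives two dates. Take 3.0, 1.8, 1.2, 0.9, 1.1, 1.4, 1.7, 2.1 g/dL. The lowest value gives progression at C6D1 and readings 1 to 3 give C7D1, which from a first response at C3D1 would be a DOR of 84 against 112 days. Under reading 4, however, 0.9 (70% reduction) is followed by 1.1 (63%), both partial response. The low is confirmed, the threshold is 1.4 under both rules, and both give C6D1. With *confirmed* undefined, the documents do not support that DOR difference as a firm result.

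A third objection is practical. The rationale for Amendment 05 in Protocol Appendix K records that ORR and secondary endpoints were analysed at the one-year cutoff and that no further efficacy data will be collected. Rewording the appendix will not change progression dates already recorded by investigators. This also stands and limits the weight of the point.

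**Conclusion.** The progressive disease row is wrong as written, and the error is minor. It conflicts with the reminder list of its own appendix and with Section 9.2.1, and for some series it gives a later progression date or none. Series 1 and 2 diverge under all four readings tried. The rules agree when the low is repeated, and also when the next visit matches its response category if *confirmed* is read that way.

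The effect is on PFS and DOR, which SAP Section 2.4.4.2 summarises without hypothesis tests, and rarely on best overall response. The worked route to best overall response depends on a value-based reading. The share of patients affected cannot be derived from the documents.

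Some stronger conclusions are tempting but unsupported. Nothing indicates that the ambiguity acts differently by arm. No effect on the ORR test has been shown. No effect on stopping treatment follows either, since Protocol Section 11.1.1 leaves discontinuation for progression to the investigator's opinion. The documents also do not show which rule investigators applied.

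**What to change.** In the progressive disease row of Protocol Appendix D, delete *confirmed* from the phrase "from lowest confirmed value in any one of the following criteria". The row, the reminder list and Section 9.2.1 then share one reference, the lowest value. Keep two-assessment confirmation of the progression event. With this change Series 1 has one answer, visit 4, and Series 2 has one answer, C5D1.

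The edit is one word, with no new data, programming or SAP analysis, plus whatever approval Protocol Section 17 requires for an amendment. It settles the definition of record. Harmonising dates already recorded would mean querying the investigators' calls, which this fix does not include.

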Appendix F Definition of relapsed and refractory myeloma

Refractory Myeloma:

Refractory myeloma is defined as disease that is non-responsive (failure to achieve minimal response or develops PD while on therapy) while on primary or salvage therapy, or progresses within 60 days of last therapy. There are 2 categories of refractory myeloma.

- Relapsed and refractory myeloma: Relapsed and refractory myeloma is defined as disease that is non-responsive while on salvage therapy or progresses within 60 days of last therapy in patients who have achieved minimal response or better at some point previously to then progressing in their disease course.
- Primary refractory myeloma: refractory myeloma is defined as disease that is non-responsive in patients who have never achieved minimal response or better with any therapy. It includes patients who never achieve MR or better in whom there is no significant change in M protein and no evidence of clinical progression; as well as primary refractory, progressive disease where patients meet criteria for true progressive disease.

Relapsed myeloma

Relapsed myeloma is defined as previously treated myeloma which progresses and requires the initiation of salvage therapy but does not meet the criteria for either primary refractory myeloma or relapsed and refractory myeloma.

(Adapted from Rajkumar VS, Harousseau J-L, et al. Consensus recommendations for the uniform reporting of clinical trials: report of the International Myeloma Workshop Consensus Panel 1. Blood. 2011;117(18):4691-95.)

Appendix G Recommended dose modification or discontinuation and supportive care guidelines for specific cemiplimab drug related adverse events

Colitis Adverse Event Management

Colitis events CTCAE v4.03	Isatuximab Dose Management	Cemiplimab Dose Management	Actions and Guidelines	Diagnostic considerations
Grade 1 Bowel obstruction Colitis Colitis microscopic	No change in dose	No change in dose	
 For diarrhea, treat symptomatically (loperamide, oral hydration, electrolyte substitution and ADA colitis diet). Endoscopy is recommended if symptoms persist. Grade 1 diarrhea that persists for >1 week should be treated with the addition of oral diphenoxylate hydrochloride and atropine sulfate four times daily and budesonide 9 mg daily. 	All attempts should be made to rule out other causes such as metastatic disease, bacterial or parasitic infection, gastroenteritis or the first manifestation of an inflammatory bowel disease by examination for stool leukocytes, stool cultures, and a Clostridium difficile titer.
Grade 2 Enterocolitis hemorrhagic Gastrointestinal (GI) perforation Necrotizing colitis Diarrhea: all patients who experience diarrhea should be advised to drink liberal quantities of clear fluids. If sufficient oral intake is not feasible, fluid and electrolytes should be substituted via IV infusion.	Delay or omit dose until ≤Grade 1 (See Section 6.5.2)	Delay or omit dose until ≤Grade 1 (See Section 6.5.2)	
 GI consultation and endoscopy is recommended to confirm or rule out colitis for Grade 2 diarrhea that persists >1 week or Grade 1-2 diarrhea with rectal bleeding (additional guidelines for the treatment of persistent colitis are provided below). Grade 2 diarrhea should be treated with addition of oral diphenoxylate hydrochloride and atropine sulfate four times daily and budesonide 9 mg daily. Grade 2 diarrhea with diffuse ulceration and bleeding seen on endoscopy may require oral steroids with prolonged taper and represent an increased risk for the development of bowel perforation. When symptoms improve to Grade 1 or less, steroid taper should be started and continued over no less than 4 weeks. In patients with Grade 2 enterocolitis, cemiplimab should be withheld and anti-diarrheal treatment should be started. If symptoms are persistent for more than 1 week, systemic corticosteroids should be initiated (eg, 0.5 mg/kg/day of prednisone or equivalent). When symptoms improve to Grade 1 or less, corticosteroid taper should be started and continued over at least 1 month. 	

Colitis events CTCAE v4.03	Isatuximab Dose Management	Cemiplimab Dose Management	Actions and Guidelines	Diagnostic considerations
Grade 3 Grade 4	Grade 3: delay or omit dose until ≤Grade 1 (See Section 6.5.2) Grade 4: discontinue treatment	Delay or Omit dose until ≤Grade 1 (See Section 6.5.2) Discontinue if unable to reduce corticosteroid dose to <10 mg/day prednisone equivalent within 12 weeks of toxicity.	
 • Patients with Grade 3 enterocolitis, drug will be permanently discontinued and treatment with systemic corticosteroids should be initiated at a dose of 1-2 mg/kg/day prednisone or equivalent. When symptoms improve to Grade 1 or less, corticosteroid taper should be started and continued over at least 1 month. • For Grade 3-4 diarrhea (or Grade 2 diarrhea that persists after initial steroid treatment): 
 - Rule out bowel perforation. Imaging with plain films or computed tomography (CT) can be useful. - Consider consultation with gastroenterologist and confirmation biopsy with endoscopy. - Treat with intravenous (IV) steroids (methylprednisolone 125 mg) followed by high dose oral steroids (prednisone 1-2 mg/kg once per day or dexamethasone 4 mg every 4 hours). When symptoms improve to Grade 1 or less, corticosteroid taper should be started and continued over no less than 4 weeks. Taper over 6-8 weeks in patients with diffuse and severe ulceration and/or bleeding. - If IV steroids followed by high-dose oral steroids does not reduce initial symptoms with 48-72 hours, consider treatment with infliximab at 5 mg/kg once every 2 weeks. Discontinue infliximab upon symptom relief and initiate a prolonged steroid taper over 45-60 days. If symptoms worsen during steroid reduction, initiate a re-tapering of steroids starting at a higher dose of 80 or 100 mg followed by a more prolonged taper and administer infliximab. CAUTION: Infliximab is contraindicated in patients with bowel perforation or sepsis. - If symptoms persist despite the above treatment a surgical consult should be obtained. 	
All attempts should be made to rule out other causes such as metastatic disease, bacterial or parasitic infection, gastroenteritis or the first manifestation of an inflammatory bowel disease by examination for stool leukocytes, stool cultures, and a Clostridium difficile titer.
 
If symptoms are persistent and/or severe, endoscopic evaluation should be considered.

Endocrine Adverse Event Management

Endocrine events CTCAE v4.03	Isatuximab Dose Management	Cemiplimab Dose Management	Actions and Guidelines	Diagnostic considerations
Grade 1-2 Hyperthyroidism Hypothyroidism Thyroid disorder Thyroiditis	No change in dose	No change in cemiplimab dose	
 Monitor thyroid function or other hormonal level tests and serum chemistries more frequently (every 3-6 weeks) until returned to baseline values. Replacement of thyroid hormone or thyroid suppression therapy as indicated. 	All attempts should be made to rule out other causes such as brain metastases, sepsis, and/or infection. An endocrinology consultation is recommended.
Grade 3-4 Hyperthyroidism Hypothyroidism Thyroid disorder Thyroiditis	Delay or omit dose until resolves to Grade \leq 2 (see Section 6.5.2)	Delay or omit dose until on stable replacement dose as determined by resolution of symptoms and normalization of hormone levels. (see Section 6.5.2)	
 Consider endocrine consultation. Rule out infection and sepsis with appropriate cultures and imaging. Replacement of thyroid hormone or thyroid suppression therapy as indicated. 	
Grade 1-4 Adrenal insufficiency Hypophysitis Hypopituitarism Pan-hypopituitarism	Grade 1, 2: no change in dose, Grade 3, 4: delay or omit dose until resolves to Grade \leq 2 (see Section 6.5.2)	Delay or omit dose until on stable replacement dose. (see Section 6.5.2)	
 Thyroid hormone and/or steroid replacement therapy to manage adrenal insufficiency. If Grade 1-2 hypophysitis is considered, pituitary gland imaging should be considered (magnetic resonance imaging [MRI] with gadolinium and selective cuts of the pituitary can show enlargement or heterogeneity and confirm the diagnosis). Grade 3-4 hypophysitis with clinically significant adrenal insufficiency and hypotension, dehydration, and electrolyte abnormalities (such as hyponatremia and hyperkalemia) constitutes adrenal crisis. Hospitalization and IV methylprednisolone should be initiated. 	All attempts should be made to rule out other causes such as brain metastases, sepsis, and/or infection. An endocrinology consultation is recommended

Pneumonitis Adverse Event Management

Pneumonitis events CTCAE v4.03 Grade	Isatuximab Dose Management	cemiplimab Dose Management	Actions and Guidelines	Diagnostic considerations
Grade 1 Pneumonitis Interstitial lung disease Acute interstitial pneumonitis	No change in Dose	Consider delay or omit dose. (see Section 6.5.2). cemiplimab may be continued with close monitoring.	
 • Radiological findings should be followed on serial imaging studies at least every 3 weeks. • Monitor for symptoms every 2-3 days. • Consider pulmonary consultation and/or bronchoscopy if clinically indicated. 	All attempts should be made to rule out other causes such as metastatic disease, bacterial or viral infection.
Grade 2 Pneumonitis Interstitial lung disease Acute interstitial pneumonitis	Delay or omit dose until resolves to Grade ≤ 1 . (see Section 6.5.2)	delay or omit dose until resolves to Grade ≤ 1 . (see Section 6.5.2)	
To rule out other causes such as infection:
 
 • Consider pulmonary consultation with bronchoscopy and biopsy/bronchoalveolar lavage (BAL). • Consider pulmonary function tests • Follow radiological findings on serial imaging studies every 1-3 days 
If the patient is determined to have study drug-associated pneumonitis
 
 • Monitor symptoms daily, consider hospitalization • Treat with systemic corticosteroids at a dose of 1-2 mg/kg/day prednisone or equivalent. When symptoms improve to Grade 1 or less, steroid taper should be started and continued over no less than 4 weeks. • Treatment with cemiplimab may be resumed if the event improves to \leqGrade 1 within 12 weeks and corticosteroids have been reduced to the equivalent of methylprednisolone 10 mg by mouth daily or less. Repeat chest imaging monthly as clinically indicated. 
For Grade 2 pneumonitis that improves to \leqGrade 1 within 12 weeks, the following rules should apply:
 
 • First episode of pneumonitis: may decrease the dose to 1 mg/kg in subsequent cycles. • Second episode of pneumonitis: Discontinue cemiplimab if upon rechallenge the patient develops a second episode of \geqGrade 2 pneumonitis. 	

Pneumonitis events CTCAE v4.03 Grade	Isatuximab Dose Management	cemiplimab Dose Management	Actions and Guidelines	Diagnostic considerations
Grade 3-4 Pneumonitis Interstitial lung disease Acute interstitial pneumonitis	Grade 3: delay or omit dose until resolves to Grade \leq 1. (see Section 6.5.2) Grade 4: discontinue treatment	Discontinue cemiplimab	
 • Consider pulmonary function tests with pulmonary consult. • Bronchoscopy with biopsy and/or BAL is recommended. • Treat with intravenous (IV) steroids (methylprednisolone 125 mg). When symptoms improve to Grade 1 or less, a high dose oral steroid (prednisone 1-2 mg/kg once per day or dexamethasone 4 mg every 4 hours) taper should be started and continued over no less than 4 weeks. • Add prophylactic antibiotics for opportunistic infections. • If IV steroids followed by high-dose oral steroids does not reduce initial symptoms with 48-72 hours, consider treatment with infliximab at 5 mg/kg once every 2 weeks. Discontinue infliximab upon symptom relief and initiate a prolonged steroid taper over 45-60 days. If symptoms worsen during steroid reduction, initiate a re-tapering of steroids starting at a higher dose of 80 or 100 mg followed by a more prolonged taper and administer infliximab. 	All attempts should be made to rule out other causes such as metastatic disease, bacterial or viral infection.

Renal Adverse Event Management

Renal events CTCAE v4.03 Grade	Isatuximab Dose Management	Cemiplimab Dose Management	Actions and Guidelines	Diagnostic considerations
Grade 1 Nephritis Nephritis autoimmune	No change in Dose	Consider delay or omit dose if event does not improve with symptomatic treatment (see Section 6.5.2)	
 • Provide symptomatic treatment. • Monitor creatinine weekly: when it returns to baseline, resume routine creatinine monitoring per protocol. 	All attempts should be made to rule out other causes such as obstructive uropathy, progression of disease, or injury to other
Grade 2 Renal failure	Delay or omit dose until resolves to Grade ≤1 (see Section 6.5.2)	Consider delay or omit dose. (see Section 6.5.2)	
 • Systemic corticosteroids at a dose of 1-2 mg/kg/day of prednisone or equivalent may be indicated. When symptoms improve to Grade 1 or less, corticosteroid taper should be started and continued for at least 1 month. • Consider prophylactic antibiotics for opportunistic infections. • Consider renal biopsy. • If elevations persist >7 days or worse, treat as Grade 4. 	chemotherapy agents. A renal consultation is recommended.
Grade 3-4 Renal failure acute	Grade 3: delay or omit dose until resolves to Grade ≤1. (see Section 6.5.2) Grade 3: discontinue treatment	Discontinue cemiplimab	
 • Renal consultation with consideration of ultrasound and/or biopsy as appropriate. • Monitor creatinine daily. • Treat with systemic corticosteroids at a dose of 1-2 mg/kg prednisone or equivalent once per day. • When symptoms improve to Grade 1 or less, steroid taper should be started and continued over no less than 4 weeks. • Discontinue cemiplimab if unable to reduce corticosteroid dose for irAEs to ≤10 mg. • Cemiplimab treatment may be restated and the dose modified as specified in the protocol. 	

Dermatologic Adverse Event Management

Skin events CTCAE v4.03	Isatuximab Dosing managment	Cemiplimab Dosing managemnt	Action and Guidelines	Diagnostic Considerations
Grade 1, 2	No change in dose	No change in dose	
Symptomatic treatment should be given such as topical glucocorticosteroids (eg, betamethasone 0.1% cream or hydrocortisone 1%) or urea-containing creams in combination with oral antipruritics (eg, diphenhrdeamine HCl or hydroxyzine HCl)
 
Treatment with oral steroids is at investigator discretion for Grade 2 events.
	All attempts should be made to rule out other causes such as metastatic disease, infectious, or allergic dermatitis.
Grade 3	No change in dose	Delay or omit dose until Grade ≤2. (see Section 6.5.2)	
Consider dermatology consultation and biopsy for confirmation of diagnosis.
 
Treatment with oral steroids is recommended, starting with 1 mg/kg prednisone or equivalent once daily or dexamethasone 4 mg 4 times per day. When symptoms improve to Grade ≤1, steroids taper should be started and continue over no less than 4 weeks.
	
Grade 4	Delay or omit dose until Grade ≤3 (see Section 6.5.2)	Discontinue treatment	
Dermatology consultation and consideration of biopsy and clinical dermatology photograph. Initiate with oral steroids with 1 mg/kg prednisone or equivalent. When symptoms improve to Grade ≤1, steroids taper should be started and continue over no less than 4 weeks.
	

Hepatitis Adverse Event Management

Hepatitis CTCAE v4.03	Isatuximab Dosing management	Cemiplimab Dosing management	Action and Guidelines	Diagnostic Considerations
Grade 1, 2	No change in dose	Delay or omit dose if there is a treatment-emergent concurrent elevation of ALT and bilirubine that corresponds to an upward shift of 2 or more grades in both parameters. (see Section 6.5.2)	Monitor liver function tests more frequently until returned to baseline values	
Grade 3, 4	Delay or omit dose until Grade ≤2 (see Section 6.5.2)	Discontinue treatment if: AST or ALT ≥5xULN Bilirubine ≥3xULN	Consider appropriate consultation and liver biopsy to establish etiology of hepatic injury, if necessary. Treat with high-dose IV glucocorticostroids for 24-48hours. When symptoms improves to Grade ≤1, a steroid taper with dexamethasone 4 mg every 4 hours or prednisone at 1-2 mg/kg should be started and continued over no less than 4 weeks. If AST/ALT levels do not decrease 48 hours after initiation of systemic steroids, oral mycophenolate mofetil 500 mg every 12 hours may be given. Infliximab is not recommended due to its potential for hepatotoxicity. Several courses of steroids taper may be necessary as symptoms may worsen when the steroid dose is decreased.	All attempts should be made to rule out other causes such as metastatic disease, progressive liver disease, viral hepatitis, alternative drug toxicity, infectious causes and/or myositis.

Ophthalmology (Uveitis) Adverse Event Management

Uveitis CTCAE v4.03	Isatuximab Dosing management	Cemiplimab Dosing management	Action and Guidelines	Diagnostic Considerations
Grade 1	No change in dose	Discontinue treatment if symptoms persist despite treatment with topical immunosuppressive therapy	Evaluation by an ophthalmologist is strongly recommended	
Grade 2	No change in dose	Discontinue treatment if symptoms persist despite treatment with topical immunosuppressive therapy, and do not improve to Grade 1 within the retreatment period or requires systemic treatment	Treat with topical steroids such as 1% prednisolone acetate suspension and iridocyclitis	All attempts should be made to rule out other causes such as metastatic disease, infection, or other ocular disease (eg, glaucoma or cataracts)
Grade ≥ 3	Delay or omit dose until Grade ≤ 2 (see Section 6.5.2)	Discontinue treatment	Treatment with systemic corticosteroids such as prednisolone at a dose of 1-2 per day. When symptoms improve to Grade ≤ 1 , steroid taper should be started and continued over no less than 4 weeks.	

Nausea and Vomiting Adverse Event Management

